APPENDIX A: STUDY TIMELINE

APPENDIX B: STUDY VISIT SCHEDULE

	Screening ²	Intervention	6 Months Post-Op ⁴
Standard Pre-operative Evaluation ¹	X		
Informed consent	X		
Breast Q Questionnaire	X		X
Randomization		X	
2D and 3D Photography	X		X
3D Simulation		X ³	
Peri and postoperative complications			X

¹ Study-relevant past medical and surgical history to be documented from consult and pre-surgical evaluation

²Screening procedures to be completed within 90 days of surgery

³Only for subjects randomized to intervention group

⁴To be performed 6 months from day of surgery ± 60 days.

3D Breast Imaging for Cosmetic and Reconstructive Breast Surgery: Does 3D Improve Patient Reported Outcomes in Primary Breast Augmentation?

NCT01964105

AUGUST 27, 2014

The trend of enrolling to the randomized arm of our study will be modeled using the LOGISTIC procedure with maximum likelihood estimation. Predicted probability will be obtained from this model to facilitate clear interpretation of non-linear relationships with time. For patient- level comparisons, the assumption of normality will be examined with the Shapiro-Wilk test after which a t-test or Wilcoxon test will be used as appropriate. When using the t-test, equality of variances will first be examined with the Folded F statistic. The pooled t-test will be used for two populations with equal variances. Otherwise the Satterthwaite t-test will be used. Breast-level comparisons will be performed using generalized estimating equations (GEE) and empirical standard error estimates to account for correlation of left and right breast measurements within the same patient. The Pearson or Spearman correlation coefficient will be used to quantify the direction and magnitude of association between mammometric, Q-Score, and clinical data. Statistical analyses will be performed in SAS, version 9.4, with descriptive statistics analyzed and graphed in Prism 7 for Mac.

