It is hoped that patients of surgeons that utilize this technology in the preoperative consultation will have significantly higher Breast Q breast augmentation module scores 6 months after surgery. "Satisfaction with care" - one of six core scales within the Breast Q - will be particularly impacted by using 3D image simulation in the consultation experience. Additionally, it is thought that superomedial pole fullness and central nipple position as quantified with mammometrics that

the 3D imaging can provide will be associated with higher Breast Q scores, especially the “satisfaction with breasts” items.

This study will represent one of the first randomized control trials performed to address patient satisfaction with breast augmentation.

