4.2 Randomization

100 patients will be recruited in the randomized cohort. Randomization will be performed by a Research Patient Coordinator and the patient assigned to the control group or the intervention group. Randomization will only occur after the patient has signed the informed consent and will be documented in the case report file as well as communicated to the treating surgeon.

Intervention group

In the intervention group, in addition to standard preoperative evaluation, 3D image simulation will be performed.

Control group

In the conventional group, only the standard preoperative evaluation will be performed.

Non-Randomized cohort

In the non-randomized cohort, the patient can choose to have the standard evaluation with the addition of the 3D image simulation or not based on discussion with their surgeon.

Minimizing measurement bias

Blinding of the patient or surgeon will not be possible due to the need for the 3D imaging simulation to be openly discussed and viewed prior to the operation for patients randomized to 3D intervention and for the nonrandomized cohort.

All subjects will be administered the Breast Q questionnaire prior to surgery regardless of assigned group. The questionnaire will take approximately 5-10 minutes of time to complete.

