4.5 Duration of Follow-Up

Patients will be followed for 6 months following their surgical procedure. Postoperative complications and adverse events will be closely monitored. Patients will be followed until resolution or stabilization of the adverse event.

At the 6 month follow-up appointment, routine postoperative 2D and 3D images will be taken for comparison to baseline. As part of this research study, the Breast Q questionnaire will be re-administered to the subject.

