7.0 STATISTICAL CONSIDERATIONS

7.1 Study Endpoints

Primary endpoint

BREAST Q Augmentation Module. This includes 6 core items, each with several sub-items. Of the 6 core items, 3 are recently shown to statistically significantly improve in patients undergoing breast augmentation: 1) satisfaction with breasts 2) psychological well-being 3) sexual well being. A fourth, 4) satisfaction with care, however, may be particularly relevant to the discerning aesthetic surgery patient using 3D imaging in consultation. The other core items in this instrument are 5) physical well-being and 6) satisfaction with overall outcome which will also be recorded.

Secondary endpoints

All patients will undergo standard 2D as well as 3D imaging before and after surgery. During consultation, and in the postoperative period, reviewing 3D imaging and morphing software will be unique to the experimental group. 3D imaging from all patients will be used to obtain mammometric data. Pre- , and post- op mammometric data (volumes, vectors, surface distances, anatomic landmarks), as well as the measurable change in these parameters before and after surgery will be correlated with changes in Breast Q patient reported outcomes scores. This will enable us to identify particular mammometric parameters that are a) associated with improved patient reported outcomes and b) determine whether certain mammometric parameters are significantly different in patients who had 3D image simulation as part of their preoperative consultation relative to those that did not.

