7.4 Data Analysis

Data analysis for this study will be descriptive in nature. Demographic and clinical characteristics of the sample, as well as post-surgery complications will be summarized using descriptive statistics and the confidence intervals will also be provided.

[figure not shown]
Patients assigned to the intervention group (3D simulation) will be compared with those who had conventional techniques using χ^2 tests for categorical variables and Student's t-tests for continuous variables. For the t-tests equal variances were not be assumed, unless significant by Levene's test. Mann-Whitney U tests will be utilized for non-normally distributed variables. Two-tailed P values 0.05 will be considered statistically significant.

Multivariate analyses for Breast Q scores, mammometric parameters, and patient satisfaction will be performed using binary logistic regression and linear regression models to examine the relationship between intervention groups and examined outcomes and to identify potential confounders. The results of multivariate analyses will be expressed as odds ratios with corresponding 95% confidence intervals. All analyses will be performed using SPSS 20.0 statistical software (SPSS Inc. Chicago, IL).

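### Baseline adjustment is not specified for the Breast Q arm comparison, although a preoperative score is collected; adding it would narrow the interval if the baseline to 6-month correlation exceeds about 0.10

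*SAP*

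**What the plan says.** **Data collected.** Protocol section 4.2: "All subjects will be administered the Breast Q questionnaire prior to surgery regardless of assigned group". Section 4.5, on the 6-month visit: "the Breast Q questionnaire will be re-administered to the subject". The visit schedule in Appendix B lists the questionnaire under screening, in the column before randomization.

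**Arm comparison.** Protocol section 7.4 says the intervention group "will be compared with those who had conventional techniques using" chi-square tests, Student's t-tests or, for non-normal variables, Mann-Whitney tests. The SAP says of patient-level comparisons that "the assumption of normality will be examined with the Shapiro-Wilk test after which a t-test or Wilcoxon test will be used as appropriate". Neither names a covariate.

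**Regression.** Section 7.4 adds: "Multivariate analyses for Breast Q scores, mammometric parameters, and patient satisfaction will be performed using binary logistic regression and linear regression models". These models are to relate intervention group to outcome and to look for confounders. No covariates are listed, and all results are to be given as odds ratios. The SAP's only models are a logistic model for the enrollment trend and GEE for breast-level measurements.

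**Form of the outcome.** The background (section 1.0) hopes that patients whose surgeons use the technology "will have significantly higher Breast Q breast augmentation module scores 6 months after surgery". The endpoint definition in section 7.1 does not say whether the arms are compared on the 6-month score or on the change. Change appears only in the secondary analysis, where mammometric data "will be correlated with changes in Breast Q patient reported outcomes scores".

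**The concern.** The baseline of a patient-reported scale often predicts its later value. When it does, a two-sample test of the 6-month score leaves explainable variation in the error term and gives a wider interval than the data allow. This trial already pays for the baseline questionnaire, so the precision would cost nothing to collect.

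The plan also leaves the form of the comparison open. The 6-month score, the change and the baseline-adjusted score are three different analyses that can give different intervals, and neither document chooses one for the primary objective.

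**Working it through.** **The plan's own figure.** The documents give no interval width, SD or correlation for Breast Q. The only related figure is in section 7.3: power above 99% for a 20 percent difference with 50 per group. It cannot be reproduced from stated inputs. If it means 20 points on a continuous score, it needs an SD of at most 20 / [(1.960 + 2.326) × √(2/50)] = 23.3. It says nothing about baseline.

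**Inputs.**
- From the protocol: 50 per arm, N = 100, 1:1 allocation (sections 7.2 and 7.3); two-sided 5% level (section 7.4).
- Assumed: correlation ρ between baseline and 6-month score from 0 to 0.7. An SD of 20 is used only to express widths in points.

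**Formula.** Compare the unadjusted 6-month comparison with a linear model on arm plus baseline, using model-based errors. Adjustment multiplies the residual variance by (1 − ρ²). Estimating the slope costs a factor of 1 + 1/(N − 4) on average, and one degree of freedom:

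width ratio = √[(1 − ρ²)(1 + 1/(N − 4))] × t(0.975, N − 3) / t(0.975, N − 2)

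At N = 100 the cost factor is √(1 + 1/96) × 1.0001 = 1.0053, so the ratio is 1.0053 × √(1 − ρ²). The unadjusted half-width at SD 20 is 1.984 × 20 × √(2/50) = 7.94 points. The last column is the unadjusted sample size per arm that would match the adjusted interval, 50 / ratio², ignoring the small change in the t quantile.

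| ρ | Width ratio | Change in width | Half-width at SD 20 | Equivalent n per arm |
|---|---|---|---|---|
| 0 | 1.005 | 0.5% wider | 7.98 | 49 |
| 0.1 | 1.000 | none | 7.94 | 50 |
| 0.2 | 0.985 | 1.5% narrower | 7.82 | 52 |
| 0.3 | 0.959 | 4% narrower | 7.61 | 54 |
| 0.5 | 0.871 | 13% narrower | 6.91 | 66 |
| 0.7 | 0.718 | 28% narrower | 5.70 | 97 |

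**Break-even.** Setting the ratio to 1 gives ρ² = 1 − 1/1.0053² = 0.0106, so ρ = 0.10. With 80 evaluable patients the break-even is 0.12, and the ratios at 0.3, 0.5 and 0.7 are 0.960, 0.872 and 0.719.

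**Check by simulation** (20,000 trials per setting, normal scores, N = 100). Mean width ratios at ρ of 0, 0.1, 0.2, 0.3, 0.5 and 0.7 were 1.005, 1.000, 0.985, 0.959, 0.871 and 0.718. The adjusted interval was the narrower one in 21%, 38%, 73%, 93%, 100% and 100% of trials.

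**If the tested value were the change.** Let k be the baseline SD divided by the 6-month SD. The large-sample variance ratio, adjusted to change, is (1 − ρ²) / (1 + k² − 2ρk). At ρ = 0.5 it is 0.92, 0.75 and 0.57 for k of 0.75, 1 and 1.25. At ρ = 0.7 it is 0.995, 0.85 and 0.63. Adjustment matches or beats the change score throughout this range, but at k = 0.75 and ρ = 0.7 the gain is nil.

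**The case against.** **A reader might infer that the plan discards the baseline.** The documents do not support that. The section 7.4 regressions could include baseline, since their covariates are simply not listed. A comparison of change scores would use it too, and nothing excludes one. The SAP sentence speaks of patient-level comparisons and names neither Breast Q nor the arms, so applying it to the primary comparison is itself an inference, though a natural one. What stands is that baseline adjustment is not specified.

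**A reader might infer bias or an invalid test.** Under 1:1 randomization the unadjusted comparison is valid. Section 7.4 also describes its analysis as descriptive, which lowers the stakes.

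**A reader might put the break-even nearer 0.2.** That value arises if HC3 robust errors are used for the adjusted model and compared with an ordinary unpooled error for the unadjusted test. At SD 20 and ρ = 0.2 both half-widths are then 7.92. With HC2 errors, the counterpart of the unpooled error, break-even returns to about 0.10 (7.92 against 7.92 at ρ = 0.1). The 0.2 reflects the choice of standard error, not a property of baseline adjustment.

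**The gain is of unknown size and may miss an important scale.** This objection stands. The correlation is not given, the gain is small below about 0.3, and only normal scores were simulated although both documents allow for non-normal data. Section 7.1 singles out one scale: "satisfaction with care, however, may be particularly relevant to the discerning aesthetic surgery patient using 3D imaging in consultation". By its name that scale may have no meaningful preoperative score, and the same may hold for satisfaction with overall outcome. Both are inferences from the names, and they are a reason to specify the model scale by scale.

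**Conclusion.** The point holds as a low-cost improvement. The named arm tests for Breast Q are unadjusted, and adjustment for the preoperative score is not specified. At the planned size the most that adjustment costs on average is an interval about 0.5% wider, if the correlation is zero. It gains from a correlation of about 0.10 upward, reaching about 13% at 0.5 and 28% at 0.7.

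These figures assume 50 evaluable patients per arm, model-based errors, normal scores and a baseline taken before randomization. They apply only to scales that have a preoperative score. The timing needs confirming: Appendix B places the questionnaire at screening, whereas section 4.2 requires only that it precede surgery, which would allow it to follow randomization and the simulation.

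**What to change.** In the SAP and protocol section 7.4:

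1. For each Breast Q scale, state whether there is a preoperative score and which value is compared between arms.
2. For each scale with a preoperative score, make the comparison in the randomized cohort a linear model of the 6-month score on assigned arm plus the baseline score completed before randomization. Report the adjusted mean difference with its 95% confidence interval. Robust errors are optional. Keep the Wilcoxon test as a sensitivity analysis.
3. For scales without a preoperative score, compare 6-month scores with the unequal-variance t-test.
4. Confirm that the baseline questionnaire precedes randomization, align section 4.2 with Appendix B, and state how a late or missing baseline is handled.
5. Report mean differences from linear models and reserve odds ratios for logistic models.

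The cost is wording and a few lines of code, with no added visits or patients. If some baselines prove to have been taken after randomization, the rule in item 4 will have to deal with them. This change does not settle which scale is primary.

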1.0 BACKGROUND AND RATIONALE

Advances in 3D breast imaging. Three-dimensional imaging, extensively utilized to provide objective outcome measures in craniofacial surgery, has been adapted for evaluation of the breast. Three-dimensional images of the breast can be used to facilitate patient education, surgical planning, as well as both a research and marketing tool by plastic surgeons. Over the past few years, investigators have identified breast measurements calculated from computerized renderings of three-dimensional photographs and documented changes in these measurements following surgical procedures such as breast reduction, breast reconstruction with implants, and breast augmentation. Changes in these parameters after operative intervention have enabled surgeon scientists to compile objective quantitative breast data, or "mammometrics" (1). Mammometric data can be statistically analyzed, longitudinally evaluated in the same patient over time, and correlated with other quantitative data including patient reported outcomes. Some of the useful mammometric measurements that can be used to quantify and compare pre- with postoperative breast surgery include total and split breast volumes, distances from the low breast crease to the nipple, and projection of the breast and nipple from the chest wall among others.

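### Superomedial pole fullness is undefined and its association with the Q-Score is planned without adjustment for breast size, so a size preference could be read as a shape effect

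*SAP*

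**What the plan says.** Protocol section 1.0 states an expectation that opens "it is thought that superomedial pole fullness and central nipple position as quantified with mammometrics that" and, after a reference to the images, concludes that these features "will be associated with higher Breast Q scores, especially the “satisfaction with breasts” items". This is a statement about the form of the breast. It bears on the secondary objective in section 2.2, which asks more generally whether mammometric parameters are associated with satisfaction.

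No passage assigns a measurement to fullness. Section 1.0 gives an open list of useful measurements, with these as examples: "include total and split breast volumes, distances from the low breast crease to the nipple, and projection of the breast and nipple from the chest". Section 7.1 lists "mammometric data (volumes, vectors, surface distances, anatomic landmarks" and says that these values and their changes "will be correlated with changes in Breast Q patient reported outcomes scores".

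On method, the SAP has one sentence: "The Pearson or Spearman correlation coefficient will be used to quantify the direction and magnitude of association between mammometric, Q-Score, and clinical data". It names no covariate and no partial correlation. Protocol 7.4 goes further: "Multivariate analyses for Breast Q scores, mammometric parameters, and patient satisfaction will be performed using binary logistic regression and linear regression models". The stated purpose of those models is to relate intervention group to outcome and to identify potential confounders. Total volume, implant size and body size are not named as covariates, and the SAP does not mention the models.

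**The concern.** A regional volume is the total volume multiplied by the share of it that lies in that region. Unless the share falls enough to offset it, a larger implant raises the regional volume even when shape is unchanged. Distances and projection may also grow with size.

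If patients simply prefer larger breasts, any such measure will correlate with satisfaction, and an unadjusted coefficient cannot show whether size or shape is responsible. A surgeon would act differently on a finding that patients like upper-pole fullness than on a finding that they like more volume. The first is what section 1.0 puts forward. Leaving the measure undefined also allows it to be chosen after the data are seen.

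**Working it through.** **The plan's own figure.** There is none for this analysis. The power above 99% in Protocol 7.3 concerns the comparison of the randomized groups and does not bear on this point.

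**Inputs from the documents.** 100 randomized patients, plus up to 50 non-randomized patients whose data also serve the secondary objective (Protocol 7.2 and 7.3), so n = 100 to 150. Two-sided 0.05 (Protocol 7.4).

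**Assumed inputs, not in the documents.** Total volume T is lognormal with coefficient of variation (CV) 30%. The superomedial share S is lognormal with CV 20-30% and independent of T. Satisfaction Y has correlation ρ = 0.2-0.4 with log T and does not depend on S. There is one value per patient and no missing data.

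**Step 1: correlation induced in the regional volume.** Let U = T × S. Under these assumptions

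corr(U, Y) = ρ × σ_T / CV_U, with σ_T = √ln(1 + 0.30²) = √0.0862 = 0.2936 and CV_U² = (1 + CV_T²)(1 + CV_S²) − 1.

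- Share CV 20%: CV_U² = 1.09 × 1.04 − 1 = 0.1336, CV_U = 0.3655, factor 0.2936/0.3655 = 0.803.
- Share CV 30%: CV_U² = 1.09² − 1 = 0.1881, CV_U = 0.4337, factor 0.2936/0.4337 = 0.677.

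**Step 2: how often that is significant.** By Fisher's transformation, the probability is about Φ(atanh(r) × √(n − 3) − 1.96), with √97 = 9.849 and √147 = 12.124.

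| ρ | Share CV | corr(U, Y) | n = 100 | n = 150 |
|---|---|---|---|---|
| 0.2 | 30% | 0.135 | 27% | 38% |
| 0.2 | 20% | 0.161 | 36% | 50% |
| 0.3 | 30% | 0.203 | 53% | 70% |
| 0.3 | 20% | 0.241 | 68% | 85% |
| 0.4 | 30% | 0.271 | 78% | 92% |
| 0.4 | 20% | 0.321 | 91% | 98% |

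Simulation under the same assumptions agrees to within about two points: 27-92% at n = 100 and 37-98% at n = 150.

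**Step 3: after adjustment.** Given T, U varies only through S, which has no effect here. The adjusted association is significant in about 5% of simulated trials, the nominal rate.

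**Step 4: is a ratio enough?** Using S unadjusted also gives about 5%, but only because S was assumed independent of T. If log S and log T correlate at 0.3 in either direction (a further assumption), corr(S, Y) is about 0.3 × 0.3 × 0.99 = 0.089 in size. The factor 0.99 is √ln(1.04)/0.20. At n = 150 that is significant in about Φ(0.0893 × 12.124 − 1.96) = 19% of trials. At 0.5, corr(S, Y) is about 0.149 and the rate is about 44%. Adjustment for T keeps it near 5% in both cases.

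**Step 5: sensitivity.** A second simulation used a log-SD of 0.25 for total volume and 0.10-0.40 for the share. Significantly positive results came in 16-96% of trials at n = 100 and 25-99.8% at n = 150. With adjustment they fell to about 2-4%, against a nominal 2.5% in one direction.

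**The case against.** A reader might infer that the trial will test fullness through absolute breast volumes and report a size preference as support for the shape hypothesis. The documents do not say that. Volume is one of four classes in 7.1, and a distance, a vector or a ratio of split to total volume would fit the text equally well. Nor does any passage say how a positive coefficient would be reported. This objection stands, so the point is conditional on the measure chosen.

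A reader might also infer that the plan ignores confounding or that the trial could never separate size from shape. Neither follows. Protocol 7.4 plans regressions partly to identify confounders, and 3D images are taken of every patient before and after surgery. Total volume is itself among the named measurements. With ρ = 0.3 and n = 150 it would be significant in about 96% of simulated trials and would have the larger coefficient in 87-93%. Many readers would therefore see size as the stronger correlate. That softens the risk but does not remove it: two unadjusted coefficients side by side still do not show whether shape adds anything once size is known.

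Fullness appears only as an expectation in the background, not in section 2.2 or 7.1. Protocol 7.4 calls the analysis descriptive, and the SAP uses correlation to quantify association. This limits the weight of the point. A descriptive coefficient of 0.135 to 0.321 where shape has no effect would still mislead.

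Finally, the documents never say that fullness is relative to breast size. Defining it as a share is therefore a choice for the investigators and cannot be read out of the text.

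**Conclusion.** The point holds as a conditional weakness that is worth correcting. Fullness has no operational definition, the SAP's only method for its association with the Q-Score is unadjusted, and no passage commits to separating shape from size. If the measure chosen grows with implant size, and satisfaction follows size alone, the unadjusted correlation would be significant in roughly 27-92% of trials at n = 100 and 37-98% at n = 150, against about 5% after adjustment for total volume.

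These rates rest wholly on the assumed CVs, the assumed correlation of 0.2-0.4 and the absence of any shape effect. The n = 150 figures also need a full non-randomized cohort with complete follow-up. The direction does not depend on the exact values; the size does. The primary comparison is unaffected.

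**What to change.** In Protocol 7.1 and the SAP:

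1. Prespecify the measure of superomedial pole fullness. The superomedial share of total volume is one option, but it does not replace the adjustment in item 2.
2. Beside the unadjusted coefficient, report the association of that measure with satisfaction with breasts adjusted for total breast volume, by partial correlation or linear regression.
3. Report total volume as a parameter in its own right.
4. Reconcile the SAP's correlation sentence with the regressions in Protocol 7.4: say whether those models apply to the mammometric associations and with which covariates.

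The images are already planned for all patients, so the cost is one derived variable, one extra analysis and a few sentences. The statistical price is some precision. Under the assumptions above, regional and total volume correlate at 0.30/0.4337 = 0.69 to 0.30/0.3655 = 0.82. Collinearity then inflates the standard error of the regional coefficient by 1/√(1 − 0.69²) = 1.4 to 1/√(1 − 0.82²) = 1.7.
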